5.0 CLINICAL INVESTIGATION DESIGN

5.1 Overall Design

This is a multi-center, open-label fixed treatment study where eligible patients will have early access, defined as within 72 hours post implantation, of the Artegraft device. A limited number of patients who opt out of the early access procedure due to patient-related factors will be followed only to 30 days post-Day 0 in this study to assess perioperative MACE and patency rates [>/= 10 days; late-access group]. Patients who sign the informed consent and fulfil the eligibility criteria will be enrolled in the clinical study. Patients with early access will be followed for 4, 12- and 26-weeks post implantation. Patients with late access will be followed to 30 days post Day 0. The late access group will also be assessed for patency at 6 months through a telephone interview or office visit to provide a more robust data set. To ensure that all required data are captured, the sites will be trained on data capture and monitored through clinic visits, hospital records, and survey calls to dialysis centers. Refer to the monitoring plan for more detail.

5.2 Scientific Rationale for Study Design

The rationale for the proposed clinical study is based on the following:

- Artegraft has been used as a successful dialysis graft for over 45 years.
- Artegraft has been used successfully with early access, defined as within 72 hours post implantation. The objective of this study in to permit Artegraft to include early access in its Instructions for use (IFU) labeling to minimize dialysis catheter use, which can lead to serious patient morbidity.
- No significant healing occurs in the initial 14-day post-implantation period.
- With early access within 72 hours), there will be a maximum of only 10 additional cannulations.
- No scientific data can be found to justify the current 10 days or recommended 14-day waiting period for vascular access grafts.
- Overall, there is minimal risk for this requested change to the IFU; most identified risks are acute, and the risks will be evaluated during this proposed clinical trial.

5.3 Clinical Investigation Population

The population for this clinical investigation will include patients who have end stage renal disease (ESRD) and require vascular access for hemodialysis.

5.4 Study Completion Definition

An early-access patient is considered to have completed the study if all phases of the study, including the 6 month visit have been completed. Study completion is when 50 patients who started with successful early access (defined by three cannulations, the first one started within 72 hours after implantation, all with minimum dialysis pump flow rates of 250 ml/min have been assessed to 6 months. In the late-access group (first access at >/= 10 days), 25 patients will be followed for 30 days post-first access [Day 0] for MACE and patency information. The late access group will also be assessed for patency at 6 months through a telephone interview or office visit to provide a more robust data set.

Artegraft, Inc. Version 4.0 21June2019
Protocol: ARTCT.BEACH.001 CONFIDENTIAL Page 31 of 81

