| Patient Number | A total of 50 patients will be randomized to early access, successfully provided early cannulation within 72 hours, and will be followed to 6 months, to provide the data required for submission to the FDA. A 12month assessment for unexpected complications will also be obtained for early access subjects. Patients randomized to the early access group who are not cannulated in the <72-hour period will be followed as a late-access subject |

Artegraft, Inc.
Protocol: ARTCT.BEACH.001

Version 4.0 CONFIDENTIAL 21June2019 Page 9 of 81

| | for 30 days after first cannulation. It is estimated that up to 10 additional patients may fall into this category. A total of 25 patients will be randomized to late access, cannulated at 10 days or later after implant and followed for at least 30 days after first cannulation [Day 0] to assess perioperative major adverse clinical events (MACE) rates and patency data. The late access group will also be assessed for patency at 6 months through a telephone interview or office visit to provide a more robust data set |
|---|---|
| Intervention Description | Patients will be implanted with the Artegraft, for vascular cannulation for hemodialysis, using standard vascular techniques, according to the Instructions for Use. |
| Number of Investigators and Study Centers | Up to five (5) investigational sites are expected to participate in the trial. |
| Study Duration | The enrollment goal is ≥3 patients per site, per month. The anticipated enrollment period is 6 months; the patient enrollment duration for early-access patients is a minimum of 6 months, and total study duration is expected to be 12 months. |
| | The follow-up period on the early access patients will be 6 months and 30 days on the late access patients. In addition, a follow-up telephone call, based on a questionnaire, will be made to the early access patients and/or dialysis centers to determine if any unexpected complications had occurred during the 6-12-month period. For this reason, all patients will be consented to 12 months. The late access group will also be assessed for patency at 6 months through a telephone interview or office visit to provide a more robust data set. |
| Primary Effectiveness Endpoint | Early access success, defined by three cannulations, the first one started within 72 hours after implantation, all with minimum dialysis flow rates of 250 ml/min pump flow rate, with a minimum 17-gauge needle. |

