- 13. History or evidence of severe peripheral arterial disease in the extremity selected for implant (i.e. arterial inflow insufficient to support hemodialysis)
- 14. History of cancer with active disease or treatment within the previous year, except for non-invasive basal or squamous cell carcinoma of the skin
- 15. Bleeding diathesis, other than that associated with ESRD
- 16. Scheduled renal transplant within 6 months
- 17. Patients who require chronic anticoagulation except for antiplatelet therapy. Patients currently receiving or who have received within the last month direct thrombin inhibitors, factor Xa inhibitors, or vitamin K antagonists should not be included in the study.

Artegraft, Inc.
Protocol: ARTCT.BEACH.001

Data Populations

All patients who receive an Artegraft implant will be included in the safety and performance analyses for the device.

The early-access group is composed of the 50 patients that are enrolled, implanted with the Artegraft, successfully provided the first cannulation within 72 hours, and are followed to 6 months. This early-access population will be used to assess Primary, Assisted Primary, and Secondary Patency at 4, 12, and 26 weeks. This early-access population also will be used to assess perioperative major adverse clinical events (MACE) rates, and all adverse events to 26 weeks.

The late-access group is composed of 25 patients that are enrolled, implanted with the Artegraft, that are first accessed at >/= 10 days, and that are followed to 30 days post Day 0. This group will be used to assess perioperative major adverse clinical events (MACE) rates and primary, assisted primary, and secondary patency, at 30 days post Day 0. The late access group will also be assessed for patency at 6 months through a telephone interview or office visit to provide a more robust data set.

Table 1a: Schedule of Assessments (SoA) Early Access Patients

| Procedure | Screening Day -45 to Day of Surgery | Day 0 [1st successful cannulation] (May occur on day of surgery) | Day 1 – 17 Days post Day 0 | Day 30 +/- 3 days post Day 0 | 12 weeks +/- 7 days post day 0 | 6 Months +/- 7 days post day 0 | 12 Months +/- 14 days post day 0* Extended Follow-up |
|--|--|---|--|--|---|---|--|
| Eligibility (inclusion/exclusion) | Х | | | | | | |
| Informed Consent | Х | | | | | | |
| Medical History | Х | | | | | | |
| Prior and concomitant medication | Х | | Х | Х | Х | Х | |
| Physical Exam | Х | | Х | Х | Х | Х | |

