3.3 Benefit/Risk Assessment

Patients who undergo implantation of the Artegraft may benefit from immediate or earlier cannulation, to limit the time required for dialysis catheter use, with the potential serious adverse effects of septicemia, sepsis, and death. The proposed change is to allow for cannulation within 72 hours post implantation. The previous label required a minimum of 10 days be allowed after implantation before puncturing the graft with needles for hemodialysis. Early cannulation may be associated with an increase in bleeding, , hemorrhage, infection, and thrombosis during initial dialysis sessions. The potential increased risks associated with early cannulation and the information to evaluate these risks are presented (Table 4).

The risks anticipated in this study are similar to those associated with currently marketed synthetic and biologic prosthetic grafts used for dialysis. The superficial site of implantation of the Artegraft, when used for dialysis, facilitates clinical and regular ultrasound monitoring of the graft, allowing any such complication to be recognized and treated promptly, thus minimizing potential risk to the patient.

More detailed information about the known and expected benefits and risks and reasonably expected adverse events (AEs) of the Artegraft are in the Instructions for Use (Package Insert) in Appendix 8. The expected adverse device and procedure effects also are listed in the Safety section and in the Informed Consent. The expected events have been derived from clinical practice, literature reviews, clinicaltrials.gov results, and FDA PMA summaries for devices of this type.

Based on the risk information (Table 4), most risks are acute and identifiable during the immediate post-implantation period. We propose a multi-center, randomized, open-label treatment trial with a primary endpoint of successful Early Access, defined by three cannulations, the first one started within 72 hours post implantation, all with minimum dialysis flow rates of 250 ml/min, with a minimum 17-guage needle. Patients having cannulation within the definition of early access (i.e., within 72 hours) will be included in the primary analysis.

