Artegraft will follow all study patients enrolled in the proposed clinical trial and that have successful cannulation within 72 hours as defined above, for 6 months. If follow-up is necessary at 1 year after graft implantation, it will be done via phone survey. The late-access group [>/= 10 days] will be followed to 30 days post-first cannulation. Day 0 is defined as the day of first cannulation, for early-access and late-access groups, to allow full follow-up to at least 30 days for both groups

Artegraft, Inc. Version 4.0 21June2019
Protocol: ARTCT.BEACH.001 CONFIDENTIAL Page 26 of 81

Table 5: Risk Analysis Associated with Early Access

| Risk | Timing of Potential Risk | Rating of Risk ¹ | Non- Clinical Testing ² | Relevant Clinical Endpoint |
|---|--|--------------------------------|--|---|
| Serious Graft Infection | Typically, between 0 (surgical or device) and 180 days (cannulation) | 3 | none | Requires Intervention |
| Serious Hemorrhage / Hematoma | Between initial cannulation and 10 days | 3 | none | Requires Intervention |
| Excessive needle hole bleeding ³ | After removal of each cannula | 1 | none | Requires Additional Direct Pressure Time |
| Occlusion; primary and secondary | Ongoing with A/V access | 3 | none | Requires Intervention ⁴ |
| Inability to Cannulate | Immediate and up to 10 days | 2 | none | Continual or need for dialysis catheter |

¹ Rating: 1=Minimal; 2=Mild; 3=Serious; 4=Life-threatening; 5=Death

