4.0 OBJECTIVES AND ENDPOINTS

Table 6: Study Objectives and Endpoints

| able 0. Study Objectives and Endpoints | | | | |
|---|---|--|--|--|
| Study Objective | The objective of the BEACH Trial is to demonstrate that early access of Artegraft is associated with acceptable rates of successful early access, and acceptable rates of a composite of adverse events, to support a modification of existing device labeling stating that Artegraft is capable of cannulation within 72 hours post implantation. | | | |
| Primary Effectiveness Endpoint | Early access success, defined by three cannulations, the first one started within 72 hours post implantation, all with minimum dialysis flow rates of 250 ml/min pump flow rate, with a minimum 17-guage needle. | | | |
| | Expectations: $^{\sim}80\%$ of patients in the early access group will have first cannulation within 72 hours. | | | |
| | Expectations: ~90% of patients receiving early access will have 3 successful cannulations. | | | |
| Primary Safety Endpoint | A composite of major adverse clinical events (MACE) including perigraft infection, hemorrhage, thrombosis, steal syndrome, and pseudoaneurysm within 30 days after first cannulation [Day 0] in the early-access and late-access groups. | | | |
| | Expectation: ~20% of patients will have at least one MACE event; no significant difference in event number or type between early and late access groups. | | | |
| | All MACE will be adjudicated by an independent accessor. | | | |
| Secondary Effectiveness Endpoints | Patency (Primary, Assisted Primary, and Secondary) at 30 days after first successful cannulation [Day 0], and at 12 weeks and 6 months after implantation in the early-access group and at 30 days post-Day 0 in the lateaccess group. The late access group will also be assessed for patency at 6 months through a telephone interview or office visit to provide a more robust data set. | | | |
| | Expectations: | | | |
| | Patency rates [all 3 types] at 30 days will be similar in the early and late access groups. | | | |
| | We expect primary patency to be ≥85%, ≥75% and ≥65% at 30 days, 3 months, and 6 months, respectively. | | | |
| | Primary-assisted patency rates at 30 days, 3 months, and 6 months will be ≥85%. | | | |
| | Secondary patency rates will be ≥90% and ≥90% at 3 and 6 months, respectively. | | | |

Artegraft, Inc.
Protocol: ARTCT.BEACH.001

Version 4.0 CONFIDENTIAL 21June2019 Page 29 of 81

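### Section 5.4 counts the 50 early-access completers by three-cannulation success, other sections count them by cannulation within 72 hours, and 6-month follow-up of early-cannulated failures is left unstated

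*Combined protocol and SAP*

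**What the plan says.** Two definitions of the same 50 patients stand in the protocol.

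- **By the outcome.** Section 5.4: "Study completion is when 50 patients who started with successful early access (defined by three cannulations, the first one started within 72 hours", with the pump-flow minimum also required and assessment to 6 months. The synopsis defines the primary effectiveness endpoint in nearly the same terms: "Early access success, defined by three cannulations, the first one started within 72 hours". Section 5.4 omits only the needle gauge.
- **By first or early cannulation.** Synopsis, Data Populations: "The early-access group is composed of the 50 patients that are enrolled, implanted with the Artegraft, successfully provided the first cannulation within 72 hours". Sections 6.8 and 9.1 likewise refer to early cannulation within 72 hours. Section 6.0 replaces only early-arm patients who were not cannulated within 72 hours. Section 5.1 follows patients with early access, defined there by the 72-hour window, to 26 weeks.

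Section 3.3 can be read either way. It assigns follow-up to enrolled patients "that have successful cannulation within 72 hours as defined above, for 6 months". The text above it speaks of "successful Early Access, defined by three cannulations, the first one started within 72 hours post implantation", but then adds: "Patients having cannulation within the definition of early access (i.e., within 72 hours) will be included in the primary analysis".

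Table 1a gives early-access patients visits at 30 days, 12 weeks and 6 months. Table 2b (cited as Table 1b in Section 10.2) gives late-access patients and early-access drop-outs a shorter schedule. It has no 12-week visit, and at 6 months there is a telephone or office contact for patency and adverse events only. The term drop-out is not defined.

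**The concern.** Take a patient first cannulated at 48 hours whose second session fails. This patient was exposed to early puncture, unlike one who missed the window. The synopsis and Sections 5.1, 6.8 and 9.1 place the patient in the 6-month cohort. Section 5.4 does not count the patient towards the 50. The narrow reading of Section 3.3 assigns no 6-month follow-up, and a site could reasonably file the patient under the undefined drop-out schedule.

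Two other provisions could turn a missed visit into a missing result. The synopsis makes 6-month follow-up part of belonging to the early-access population: "successfully provided the first cannulation within 72 hours, and are followed to 6 months". Section 9.2.8 limits the effectiveness population to patients with responses reported.

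Section 9.1 tests no hypothesis and compares observed rates numerically with expected and published ones. The point estimate therefore carries the evidence for the label change, and its denominator should not depend on success on the trial's own endpoint.

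**Working it through.** **The plan's own figure.** The 50 has no formula behind it; Sections 6.8 and 9.1 call it logistical. The one related figure is the allowance of up to 10 further early patients who miss the window, 60 in all. At the roughly 80% first-cannulation rate in Section 4.0, 50 / 0.80 = 62.5, so 63. The stated 60 equals 50 × 1.20 and corresponds to a rate of 50 / 60 = 83%. It contains nothing for three-cannulation failures.

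**Inputs.**
- Success among those accessed early, Section 4.0: about "90% of patients receiving early access will have 3 successful cannulations".
- Expected 6-month patency, Section 4.0: primary at least 65%, secondary at least 90%.
- Patency among endpoint failures: not given. Assumed to lie between zero and that of the successes.

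**Patients outside the counted 50 if Section 5.4 governs.** Needed = 50 / success rate, rounded up.

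| Success rate | Cannulated early | Outside the 50 |
|---|---|---|
| 95% (assumed) | 52.6 → 53 | 3 |
| 90% (plan) | 55.6 → 56 | 6 |
| 85% (assumed) | 58.8 → 59 | 9 |

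If the 50 are counted by first cannulation, about 50 × 0.10 = 5 of them miss the endpoint and stay in the 6-month cohort. Randomised to early access: 63 on that count, against 50 / (0.80 × 0.90) = 69.4, so 70, under Section 5.4.

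**Effect on a successes-only 6-month rate.** Let P be patency in all early-cannulated patients, S in successes and q in failures. Then P = 0.9 S + 0.1 q, so S = (P − 0.1 q) / 0.9.

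| q | S when P = 65% (primary) | S when P = 90% (secondary) |
|---|---|---|
| 0% | 72.2% (+7.2) | 100% (+10.0) |
| 25% | 69.4% (+4.4) | 97.2% (+7.2) |
| 50% | 66.7% (+1.7) | 94.4% (+4.4) |
| equal to P | 65.0% (0) | 90.0% (0) |

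In the other direction, if the successes sit exactly at expectation and no failure is patent, the whole-cohort rates are 0.9 × 65% = 58.5% and 0.9 × 90% = 81%. That is the extreme case.

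**The case against.** A reader might infer that the plan follows and analyses only early successes, so that exposed failures leave the 6-month safety and patency data. The documents do not support that.

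- Section 5.4 says when the study is complete, not who is followed or analysed. Its first sentence, on when an individual early-access patient completes, carries no three-cannulation condition.
- The sentence nearest to the Section 3.3 follow-up rule describes early access by the 72-hour window alone.
- Missing the three-cannulation endpoint is nowhere a trigger for replacement. The synopsis sends to late-access follow-up only those not cannulated in the window, which suggests what drop-out was meant to mean.
- The Safety population is every implanted patient (Section 9.2.7), all safety analyses use it (Section 10.2.8), and data from withdrawn patients are kept (Section 10.2.9). Even the reduced schedule has a 6-month patency and adverse-event contact.

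Nor are 81% and 58.5% estimates of the true rates. They assume that every failure is removed from the analysis and that none is patent. The endpoint can be missed on pump flow or needle gauge without loss of the graft. Patency runs from access placement and is estimated by Kaplan-Meier (Sections 3.2 and 9.2.3), so a thrombosis at the second session is an event on that day if the patient stays in the analysis. At n = 50 the standard error of a 65% rate is √(0.65 × 0.35 / 50) = 6.7 points, about the size of the worst primary-patency case.

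All of this stands, and it limits the point. It shows what most of the protocol intends. It does not remove the conflicting sentence in Section 5.4, settle Section 3.3, or state a schedule for the early-cannulated failure.

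**Conclusion.** This is an internal inconsistency that should be fixed. Section 5.4 makes the completion count depend on success on the primary endpoint, and Section 3.3 can be read the same way for follow-up, against the synopsis and Sections 5.1, 6.0, 6.8 and 9.1.

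If Section 5.4 and the narrow reading of Section 3.3 were followed, about 6 of 56 early-cannulated patients (3 of 53 to 9 of 59 at assumed success rates of 95% to 85%) would be outside the counted 50 and could miss the 12-week and 6-month visits. A 6-month rate reported on successes only would then be too favourable by 0 to about 7 points for primary patency and 0 to about 10 points for secondary patency. These are bounds. They rest on the plan's 90%, on its patency expectations holding in the whole early-cannulated cohort, and on the assumed range for patency among failures.

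The 30-day MACE endpoint and membership of the Safety population are not affected; at issue are the 6-month results. The higher enrolment implied by Section 5.4 is a separate consequence and no evidence of selective follow-up.

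**What to change.** Three changes of wording:

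1. In Section 5.4, define completion as the 6-month assessment, or earlier death, withdrawal or loss to follow-up, of the early patients whose first cannulation was started within 72 hours, whether or not the three-cannulation endpoint was met.
2. In Section 3.3, replace the condition "that have successful cannulation within 72 hours as defined above, for 6 months" with a first cannulation started within 72 hours, keeping the 6-month period.
3. State that Table 1a applies to all of these patients, and that missing the endpoint triggers neither replacement nor the reduced schedule. This also settles that they are not early-access drop-outs.

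The cost is a short amendment. About 5 or 6 patients stay on the full visit schedule that the synopsis already implies, and reported patency may be slightly less favourable. Enrolment would be smaller than Section 5.4 now implies (about 63 rather than 70 randomised early). No rule on cannulation changes. The amendment should precede follow-up, because missed 12-week and 6-month visits cannot be recovered.

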6.0 PATIENT SELECTION AND WITHDRAWAL

Prospective approval of protocol deviations to recruitment and enrollment criteria, also known as protocol waivers or exemptions, is not permitted.

A protocol deviation is any noncompliance with the protocol or GCP requirements. The noncompliance may be either on the part of the participant, the investigator, or the study site staff. If there are protocol deviations, corrective actions are to be developed by the site and implemented promptly. Although it is in principle not allowed to deviate from the protocol, under emergency circumstances, deviations may proceed without prior approval of the sponsor and the IRB to protect the rights, safety, and well-being of human subjects.

All protocol deviations, with no regard if they are assessed as major or minor, will be documented and reported by the CRO during the study in the Monitoring Reports. Major deviations will be reported to the sponsor who will agree on the necessary actions to be taken. If required per their guidelines, reports about protocol deviations must be reported to the local IRB.

Any patients in the late access group who require cannulation prior to the 10-day cannulation period will receive Standard of Care treatment. Dialysis will be initiated using an existing dialysis catheter or after placement of a new dialysis catheter. Hemodialysis with Artegraft will commence after the 10-day waiting period.

Any patients that are in the early access group that are not cannulated within 72 hours shall be replaced by additional patients using the randomization plan until the 50-patient number is reached.

